8.5.2 Description of Activities

The following data will be documented (if assessed in routine care):

Physician:

Baseline Visit (Month 0)

Demographics and History

Demographic Data (age, gender, height, weight)

Inclusion criteria (moderate to severe active RA and/or severe, active, and progressive RA, signed informed consent)

Exclusion criteria according to Fachinformation (hypersensitivity, active tuberculosis, other severe infections [e.g. sepsis, opportunistic infections], moderate to severe heart insufficiency [NYHA class III/IV])

HUMIRA®
AGIL

Indication for the current HUMIRA® therapy

Radiological findings of affected joints

History (including initial diagnosis of RA and tobacco use)

Previous therapies: DMARD (MTX, SASP, leflunomid), glucocorticoids, biologics (infliximab, etanercept, rituximab, tocilizumab, abatacept), date of biologic discontinuation

Concomitant diseases and concomitant medication

Current RA therapy

Current HUMIRA® therapy

Additional DMARD, systemic glucocorticoids, analgetics, NSAID, COX inhibitors

Current status

Disease activity, joint status (28 joints, tender, swollen), morning stiffness, rheumatoid nodules, previous joint surgery

Laboratory values (RF, CCP, CRP, ESR, Hb-value, hepatitis B, hepatitis C, tuberculosis screening, TB prophylaxis, pregnancy test in women with childbearing potential)

Follow-up Visits (Month 3, 6, 12, 24, 36, 48, 60)

Change history

Current therapy (RA therapy and concomitant medication)

Disease activity

Joint status

Morning stiffness

Joint (replacement) surgery (beginning month 12)

Radiographic findings (beginning month 12)

Laboratory values (CRP, ESR, Hb-value, other laboratory values if indicated)

(S)AE

Patient's compliance

Patient:

Baseline Visit (Month 0)

Personal data

Education

Professional status

Missed working days, days of impairment in non-occupational activities

Physician visit, hospitalization

WPAI, HAQ, and EQ-5D

Exhaustion/Fatigue, pain
Participation in the Abbott Care service program

Follow-up Visits (Month 3, 6, 12, 24, 36, 48, 60)

WPAI, HAQ, and EQ-5D
Exhaustion/Fatigue, pain
Patient's assessment of adalimumab therapy
Participation in the Abbott Care service program

Follow-up Visits (Month 6, 12, 24, 36, 48, 60)

As above, additionally:
Missed working days, days of impairment in non-occupational activities
Physician visits, hospitalization
Changes in the professional status

8.5.3 Scales and Scores

The following scores will be derived from the documented data:

Disease Activity Score (DAS28): The DAS28 indicates the severity of the RA. The score varies between 0 and 10, with 10 indicating the highest degree of severity. The DAS28 is calculated from the following data documented on the physician form:

- Joint status: Number of swollen and tender joints (each with a maximum of 28)
- ESR (mm/1. h) or CRP (mg/l)
- Patient's assessment of current disease activity (from 0 = inactive to 10 = highly active)

The DAS28 is calculated by means of a validated algorithm (4), (5).

Health Assessment Questionnaire (HAQ): The HAQ is the internationally most-used instrument for assessing RA-related functional impairment. The patient has to answer 20 questions concerning impairment in daily activities within the following 8 areas:

- Dressing & Grooming
- Arising

- Eating
- Walking
- Hygiene
- Reach
- Grip
- Activities

Patients assess their functionality over the past week by means of a 4-level scale ranging from 0 (without any difficulty) to 3 (unable to do). The highest (worst) values will be calculated into a mean value which indicates the degree of functional impairment (HAQ Disability Index: 0-3) (8).

WPAI: The WPAI is a questionnaire for the self-assessment of work productivity and activity impairment. In this observational study, the WPAI-GH is used which measures work productivity and activity impairment with reference to general health problems. All dimensions relate to the past seven days. The following dimensions are measured:

- Assessment of employment status
- Assessment of hours missed from work due to health problems and other reasons such as vacation or holidays (total number of hours to be indicated)
- Assessment of hours the patient has actually worked (total number of hours to be indicated)
- Assessment of impairment in work productivity and in regular daily activities (2 assessments with 10 levels each)

The WPAI yields four types of scores:

- ‘activity impairment’
- ‘absenteeism’ (work time missed)
- ‘presenteeism’ (impairment at work/reduced on-the-job effectiveness) and
- ‘work productivity loss’ (overall work impairment/absenteeism plus presenteeism).

Scores were transformed into percentages. Higher scores indicate greater impairment.

EuroQol-5 Dimensions (EQ-5D): The EQ-5D is a generic (not disease specific) instrument for measuring health-related quality of life. The patient questionnaire consists of two parts. The first part includes statements for the following five areas (dimensions):

- agility/mobility
- self-care
- usual activities
- pain, bodily discomfort
- anxiety, depression

For each dimension the patient is asked for a three-level assessment of his health on the current day: “no problems” (1), “some problems” (2), “extreme problems” (3). From the possible combinations of the five three-level areas result 241 different health-statuses.

The second part is a thermometer-scale (EQ-VAS) on which the patients rate their health on the current day between the endpoints “best health imaginable” (100) and “worst health imaginable” (0).

8.5.4 Study Medication

This is a non-interventional observational study with HUMIRA®. HUMIRA® is used according to the approved label for rheumatoid arthritis and is prescribed by the attending physician. Abbott does not provide any study medication.

HUMIRA®-injection is available as ready-to-use syringes and as pre-filled pen (injector, pre-filled/FertigPEN) and includes 40 mg adalimumab.

The recommended dose of HUMIRA® for adult patients with RA is 40 mg sc every other week.

9 Adverse Events

9.1 Adverse Event Definition and Serious Adverse Event Categories

An adverse event (AE) is defined as any untoward medical occurrence in a patient which does not necessarily have a causal relationship with their treatment. An adverse event can therefore be any unfavorable and unintended sign (including an abnormal laboratory finding), symptom, or disease temporally associated with the use of a medicinal product, whether or not the event is considered causally related to the use of the product.

Such an event can result from use of the drug as stipulated in the labeling, as well as from accidental or intentional overdose, drug abuse, or drug withdrawal. Any worsening of a pre-existing condition or illness is considered an adverse event.

If an adverse event meets any of the following criteria, it is considered a **serious adverse even (SAE)**:

Death of Subject: An event that results in the death of a subject.

Life-Threatening: An event that, in the opinion of the investigator, would have resulted in immediate fatality if medical intervention had not been taken. This does not include an event that would have been fatal if it had occurred in a more severe form

Hospitalization: An event that results in the admission to the hospital for any length of time. This does not include an emergency room visit or admission to an outpatient facility.

Prolongation of Hospitalization: An event that occurs while the study subject is hospitalized and prolongs the subject's hospital stay.

Congenital Anomaly: An anomaly detected at or after birth that results in fetal loss.

Persistent or Significant Disability/Incapacity: An event that results in a condition that substantially interferes with the activities of daily living of a study subject. Disability is not intended to include experiences of relatively minor medical

significance such as headache, nausea, vomiting, diarrhea, influenza, and accidental trauma (e.g., sprained ankle).

Important Medical Event Requiring Medical or Surgical Intervention to Prevent Serious Outcome: An important medical event that may not be immediately life-threatening or result in death or hospitalization, but based on medical judgment may jeopardize the subject and may require medical or surgical intervention to prevent any of the outcomes listed above (i.e., death of subject, life-threatening, hospitalization, prolongation of hospitalization, congenital anomaly, or persistent or significant disability/incapacity). Examples of such events include allergic bronchospasm requiring intensive treatment in an emergency room or at home, blood dyscrasias or convulsions that do not result in inpatient hospitalization, or the development of drug dependency of drug abuse.

Spontaneous Abortion: Miscarriage experienced by study subject.

Elective Abortion: Elective abortion performed on study subject.

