9.6 Pregnancy Reporting

In the event of a pregnancy, the physician will notify the Abbott drug safety identified below within 24 hours of the physician becoming aware of the pregnancy. The notification will be performed via fax on the base documentation form:

Reported pregnancies will be reported like SAEs.

10 Ethics and Quality

In accordance to the code of conduct of the German pharmaceutical industry, the German principal coordinating investigator [REDACTED] will forward the NIS study protocol to the ethics committee for approval:

The patient has to provide a written informed consent to use and/or disclose personal and/or health data before enrollment in the study. This written informed consent will be archived with the patient's file and documented on the report forms. According to § 67 section 6 AMG, the NIS will also be reported to the Kassenärztliche Bundesvereinigung (federal association of physicians), the umbrella organization of health insurance providers, and the responsible federal authority.

All patient data entered in the patient's CRF will be forwarded to Abbott GmbH & Co KG for evaluation - without naming the patient. Each CRF bears a pre-printed patient identification number, which replaces the patient's initials. The date of birth will be replaced by the patient's age at the start of the study. Accordingly, the patient's identity will not be disclosed to Abbott GmbH & Co. KG.

In-house monitoring of incoming CRF pages with respect to completeness and plausibility will be done by the CRO responsible for data management and statistics. Queries to the study centers will be handled by the sponsor.

Source data verification by the sponsor's monitor at the physician's site is planned for 5% of the documented patients. Informed consent, in- and exclusion criteria, and all available source data will be inspected.

HUMIRA®
AGIL

This NIS will be sponsored by Abbott GmbH & Co. KG, [REDACTED]

[REDACTED]

11 Case Report Form

All data specified in Section 8.5 will be collected on paper forms (CRF). For each visit, the CRF includes forms to be completed by the physician as well as forms to be completed by the patient. Each center receives a folder with all documents and forms necessary for the baseline and follow-up documentation of five patients.

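### The congenital anomaly criterion in Section 9.1 joins two conditions that together exclude every anomaly in a live-born child, and the pregnancy reporting text does not close that gap.

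*Combined protocol and SAP*

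**What the plan says.** All references are to the combined protocol and SAP.

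- **Section 9.1, the criterion:** a congenital anomaly is defined as "An anomaly detected at or after birth that results in fetal loss".
- **Section 9.1, how the criteria combine:** the list opens with "If an adverse event meets any of the following criteria, it is considered a" serious adverse event. One criterion is enough.
- **Section 9.1, whose event counts:** an adverse event is "any untoward medical occurrence in a patient which does not necessarily have a causal relationship with their treatment".
- **Section 9.1, disability criterion:** "An event that results in a condition that substantially interferes with the activities of daily living of a study subject".
- **Section 9.1, important medical event criterion:** it refers back to the serious outcomes already listed, among them "prolongation of hospitalization, congenital anomaly, or persistent or significant disability/incapacity". No condition about fetal loss is attached here.
- **Section 9.1, pregnancy loss:** "Spontaneous Abortion: Miscarriage experienced by study subject" is a separate criterion, and elective abortion is another.
- **Section 9.4:** SAE collection ends 30 days or 5 half-lives after the last dose.
- **Section 9.6:** the physician notifies drug safety within 24 hours of learning of a pregnancy, using the base documentation form, and "Reported pregnancies will be reported like SAEs". The text does not mention the outcome of the pregnancy or the child.

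**The concern.** The usual purpose of a congenital anomaly category is to make sure that an affected child is classed and reported as a serious event. As worded, the category requires fetal loss as well, and a live birth rules that out. The outcome for which a separate category is most needed is therefore the one left out.

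Safety evaluation through adverse events and SAEs is a stated target (Synopsis and Section 7). The plan expects women who may become pregnant, since a pregnancy test is on the baseline list in Section 8.5.2. About 2500 patients are to be documented for up to five years each. A site that applies the text literally could leave a live-born child's anomaly off the SAE form and outside the 24-hour notification in Section 9.5. The event would then be missing from the SAE incidence rates planned in Section 12.5. Such events would be few, so each one missed or misclassified would matter.

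**Working it through.** No arithmetic applies and the plan gives no figure to reproduce. The check is a reading of the criterion case by case, followed by a search for another route that would catch what it misses.

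**Step 1. Apply the two conditions.** Let A be that the anomaly is found at delivery or later, and B that it leads to loss of the fetus. The wording requires A and B together.

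| Case | A | B | Criterion met? |
|---|---|---|---|
| (a) Live birth, anomaly found at or after birth | yes | no | no |
| (b) Anomaly found before birth, then fetal loss | no | yes | no |
| (c) Anomaly found before birth, then live birth | no | no | no |
| (d) Stillbirth, causal anomaly first found at or after delivery | yes | yes | yes, if delivery of a stillborn counts as birth |

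Both live-birth cases, (a) and (c), fail. Only (d) can pass.

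**Step 2. Look for another criterion in Section 9.1.** Because one criterion suffices, an event that fails here may be serious elsewhere.

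- Case (b) is largely covered: a miscarriage or elective abortion is serious under its own criterion. At most, a late loss that nobody calls a miscarriage remains.
- Cases (a) and (c) are not plainly covered. The adverse event definition speaks of the patient. The disability criterion speaks of the study subject, and the important medical event criterion depends on jeopardy to the subject. None of them mentions a child.
- The hospitalization criterion might catch some cases if a site treats the child's admission as the patient's event. An anomaly without an admission would still be missed.

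**Step 3. Compare the two uses of the term within Section 9.1.** The definition carries the fetal-loss condition. The important medical event criterion refers back to congenital anomaly as a listed serious outcome without that condition. A site reading the first would not class a live-born child's anomaly as serious, and a site reading the second could.

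**Step 4. Check pregnancy reporting and timing.** Section 9.6 is triggered by awareness of the pregnancy. Treating the pregnancy like an SAE does not by itself ask for an anomaly discovered months later. Section 9.4 closes SAE collection 30 days or 5 half-lives after the last dose, and under Section 8.4 documentation ends when adalimumab ends or after five years. If treatment stops early in a pregnancy, the birth can fall after both limits. The documents give no half-life, so the exact length of the window cannot be worked out from them.

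**The case against.** Four points can be made on the other side.

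1. **The criterion is not empty.** A reader might infer that the two conditions exclude each other and that no event can ever qualify. The documents do not support this, because case (d) satisfies both. This objection stands, and the claim must be limited to live births plus the residual part of case (b).

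2. **Fetal losses are mostly handled elsewhere.** A reader might infer that every congenital anomaly escapes classification as serious. That is also too strong, because miscarriage and elective abortion are separate criteria. This stands.

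3. **Sites would understand what is meant.** The category is headed congenital anomaly, the term appears later without the condition, and Section 9.1 contains other slips of wording. A lost *or* between the two conditions is a plausible explanation. It remains a guess, since nothing in the documents shows the intended text, and an operative reporting rule should not depend on sites reading past it.

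4. **Drug safety hears of the pregnancy anyway.** Section 9.6 requires prompt notification of any pregnancy, so the sponsor is alerted to the exposure. A reader might infer that pregnancy outcomes are never collected. That cannot be shown, because the form named in Section 9.6 is not among the documents and its fields cannot be judged. What can be said is that the text of Section 9.6 does not ask for the outcome. This softens the practical consequence but does not repair the definition.

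**Conclusion.** The definition is wrong as written. Read literally, it excludes every anomaly in a live-born child, it conflicts with the unqualified use of the term in the same section, and no other section corrects it. The remaining routes to classification as serious depend on a site's judgment or on an admission to hospital.

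The conclusion rests on reading the sentence as a conjunction, which is its plain grammar, and on taking fetal loss to mean that the pregnancy did not end in a live birth. Whether case (d) qualifies depends further on counting delivery of a stillborn as birth.

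The size cannot be given as a number, because the documents contain no expected count of pregnancies or of anomalies. The effect is confined to safety classification, expedited reporting and the SAE incidence rates. No efficacy analysis, power statement or sample size is touched.

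**What to change.** Reconcile Sections 9.1, 9.4 and 9.6.

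- **Section 9.1, criterion:** state the two conditions as alternatives: an anomaly found at or after birth, or an anomaly that leads to loss of the fetus. This also brings the definition into line with the important medical event criterion.
- **Section 9.1, scope:** add that an anomaly in a patient's child counts, since the adverse event definition refers only to the patient. Without this, rewording the criterion leaves open whether the child's anomaly is an adverse event at all.
- **Section 9.6:** require the outcome of every reported pregnancy to be reported by the SAE route, and name the form. The section currently points to the base documentation form, which is not the SAE form named in Section 9.5.
- **Sections 9.4 and 9.6:** state how outcome reporting applies when the birth falls after the SAE collection period.

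The cost is a few sentences, plus a check that the forms match them. No analysis or sample size has to be reworked.

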9.2 Severity

The physician will use the following definitions to rate the severity for any adverse event being collected as an endpoint/data point in the study and for all serious adverse events:

Mild: The adverse event is transient and easily tolerated by the subject.

Moderate: The adverse event causes the subject discomfort and interrupts the subject's usual activities.

Severe: The adverse event causes considerable interference with the subject's usual activities and may be incapacitating or life-threatening.

9.3 Relationship to Pharmaceutical Product

The physician will use the following definitions for any adverse event being collected as an endpoint/data point the study and for all serious adverse events, to assess the relationship of the adverse event to the use of the pharmaceutical product:

Probably related: An adverse event has a strong temporal relationship to the study drug or recurs on re-challenge, and another etiology is unlikely or significantly less likely.

Possibly related: An adverse event has a strong temporal relationship to the study drug, and an alternative etiology is equally or less likely compared to the potential relationship to study drug.

Probably not related: An adverse event has little or no temporal relationship to the study drug, and/or a more likely alternative etiology exists,

Not related: An adverse event is due to an underlying or concurrent illness or effect of another drug and is not related to the study drug (e.g., has no temporal relationship to study drug or has a much more likely alternative etiology).

If an investigator's opinion of possibly, probably not, or not related to pharmaceutical product is given, **an alternate etiology must be provided by the investigator.**

9.4 Serious Adverse Event Collection Period

Serious adverse events will be reported to Abbott from the time the physician obtains the patient's authorization to use and disclose information (or the patient's informed consent) until 30 days or 5 half-lives following the intake of the last dose of physician-prescribed treatment.

9.5 Serious Adverse Event Reporting

In the event of a serious adverse event – whether or not related to Abbott product or comparator, if applicable – the physician will notify the Abbott drug safety identified below within 24 hours of the physician becoming aware of the event. The notification will be performed via fax on the form labeled “Bericht über Schwerwiegende Unerwünschte Arzneimittelwirkungen”:

9.6 Pregnancy Reporting

In the event of a pregnancy, the physician will notify the Abbott drug safety identified below within 24 hours of the physician becoming aware of the pregnancy. The notification will be performed via fax on the base documentation form:

Reported pregnancies will be reported like SAEs.

10 Ethics and Quality

In accordance to the code of conduct of the German pharmaceutical industry, the German principal coordinating investigator [REDACTED] will forward the NIS study protocol to the ethics committee for approval:

The patient has to provide a written informed consent to use and/or disclose personal and/or health data before enrollment in the study. This written informed consent will be archived with the patient's file and documented on the report forms. According to § 67 section 6 AMG, the NIS will also be reported to the Kassenärztliche Bundesvereinigung (federal association of physicians), the umbrella organization of health insurance providers, and the responsible federal authority.

All patient data entered in the patient's CRF will be forwarded to Abbott GmbH & Co KG for evaluation - without naming the patient. Each CRF bears a pre-printed patient identification number, which replaces the patient's initials. The date of birth will be replaced by the patient's age at the start of the study. Accordingly, the patient's identity will not be disclosed to Abbott GmbH & Co. KG.

In-house monitoring of incoming CRF pages with respect to completeness and plausibility will be done by the CRO responsible for data management and statistics. Queries to the study centers will be handled by the sponsor.

Source data verification by the sponsor's monitor at the physician's site is planned for 5% of the documented patients. Informed consent, in- and exclusion criteria, and all available source data will be inspected.

HUMIRA®
AGIL

This NIS will be sponsored by Abbott GmbH & Co. KG, [REDACTED]

[REDACTED]

11 Case Report Form

All data specified in Section 8.5 will be collected on paper forms (CRF). For each visit, the CRF includes forms to be completed by the physician as well as forms to be completed by the patient. Each center receives a folder with all documents and forms necessary for the baseline and follow-up documentation of five patients.

Any observation of an adverse event in the time period up to 60 months, beginning with the initiation of HUMIRA® therapy, is to be documented on the "Adverse Event" form labeled 'Bericht über unerwünschte Ereignisse' and checked for severity. If the event fulfills the serious criterion (Serious Adverse Event), the "Adverse Drug Reaction Report" form labeled 'Bericht über Schwerwiegende Unerwünschte Arzneimittelwirkungen' is to be completed additionally.

12 Data Analysis Plan

All statistical analysis procedures will be described in detail in a Statistical Analysis Plan (SAP). This plan will be developed by the responsible biometrist in collaboration with the sponsor. The SAP will be finalized and approved by the responsible biometrist, the sponsor, and the principle investigator before the database will be opened for the first interim analysis.

